4.1 ANALYSIS POPULATIONS

In the study, two populations are distinguished: Safety Population and Intent-To-Treat (ITT) Population. The analysis for the iDMC will be provided based on the Safety Population.

4.1.1 Randomized Population

Not applicable.

4.1.2 Per Protocol Population

Not applicable for the analyses described in this SAP.

4.1.3 Pharmacokinetic-Evaluable Population

Not applicable for the analyses described in this SAP.

4.1.4 Safety Population

The analysis population for this study will include all enrolled patients who have received at least one dose of atezolizumab. The safety population will be used for all baseline and safety analyses, unless otherwise stated.

4.1.5 Intent-to-treat population

The ITT population will include all patients who have signed informed consent and met all eligibility criteria. The ITT population will be used for all efficacy analyses, unless otherwise stated. (According to the Protocol, should the difference between the ITT and safety populations have been 5 or fewer patients – which was not the case –, all efficacy analyses would have been based only on the safety population).

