### **1.3.3 Efficacy**

[figure not shown]
IMvigor 210 (Study GO29293) is a single-arm, open-label, Phase II study to assess the clinical benefit of atezolizumab as a single agent in patients with locally advanced or metastatic UC. The co-primary endpoints of the study were IRF-assessed ORR according to RECIST v1.1 and investigator-assessed ORR according to modified RECIST criteria. Results from Cohort 2, which contained patients whose disease had progressed after previous platinum-based chemotherapy (see Section 1.3.2), were recently published ([Rosenberg et al. 2016](#)).

Between 13 May 2014, and 19 Nov 2014, 486 patients were screened and 316 patients were enrolled into IMvigor 210. Of these, 311 patients received atezolizumab treatment (five enrolled patients later did not meet eligibility criteria and were not dosed with study drug).

The primary analysis (data cutoff 05 May 2015) showed that treatment with atezolizumab resulted in significantly improved ORR for each pre-specified immune cell group when compared with a historical control ORR of 10% (IC2/3: 27% [95% CI 19–37%],  $p<0.0001$ ; IC1/2/3: 18% [13–24%],  $p=0.0004$ ). The same was true for the entire population of patients (15% [11–20],  $p=0.0058$ ). With longer follow-up by independent review (data cutoff 14 September 2015), ORRs were 26% (95% CI 18–36%) in the IC2/3 group, 18% (13–24%) in the IC1/2/3 group, and 15% (11–19%) overall in all 310 patients. Ongoing responses were recorded in 38 (84%) of 45 responders after a median follow-up of 11.7 months (95% CI 11.4–12.2 months).

Further details of the response to atezolizumab in IMvigor 210 are presented in [Figure 1](#).

**Figure 1. Change in Sum of the Diameters Over Time by Best Response in the PD-L1 IC2/3 group and Overall Survival in PD-L1 Immune Cell Groups**

IC = immune cell

Note: The above figure presents the percentage change in the sum of longest diameters by IRF-assessed RECIST v1.1 in the IC2/3 group by (A) responders, (B) patients with stable disease, and (C) patients with progressive disease. Patients without a measurable baseline tumor assessment or without post-baseline tumor measurements were not included. (D) Kaplan-Meier overall survival curves for the IC0, IC1, and IC2/3 groups.

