### **Analysis populations**

This study will include the following analysis populations:

- **Safety population**: The primary analysis population for this study will include all enrolled patients who have received at least one dose of atezolizumab. The safety population will be used for all baseline and safety analyses, unless otherwise stated
- **Intent-to-treat population**: The intent-to-treat (ITT) population will include all enrolled patients. The ITT population will be used for all efficacy analyses, unless otherwise stated. In case the difference between the ITT and safety populations is 5 or fewer patients, all efficacy analyses will be based only on the safety population

A per-protocol population will not be defined for this study. However all major deviations (at study entry and on study) will be summarized and reported.

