4.2 ANALYSIS OF STUDY CONDUCT

Disposition of patients

Patients will be considered as having treatment discontinued when the “Study Completion/Early Discontinuation” has been captured for the treatment phase.

Patients will be considered as having discontinued/completed the study when the “Study Completion/Early Discontinuation” has been captured for the follow-up phase or the treatment phase and it was indicated as the final study period.

The disposition of patients will be summarized as follows:

Enrolled patients:

- Number of patients who signed informed consent and met all eligibility criteria, i.e. number of patients in the ITT Population

- Number and percentage of patients who have received at least one dose of atezolizumab, i.e. number and percentage of patients in the Safety Population (out of the ITT Population)
- Number and percentages of patients who have permanently discontinued atezolizumab, overall and by reasons for discontinuation (out of the Safety Population)
- Number and percentages of patients who have permanently discontinued atezolizumab by cycle and by reasons for discontinuation (out of the Safety Population). Discontinuations will be associated with the number of cycles the patient received, a cycle being counted when dose >0. A summary table and figure will be provided.
- Number and percentages of patients who have discontinued the study, overall and by reasons for discontinuation (out of the ITT Population)
- Number and percentages of patients by region, country and site number (out of the ITT population and Safety population)

Following by-patient listing including site, patient identifier and relevant data will be provided:

- Enrolled patients

Protocol violations

A by-patient listing of major protocol violations will be provided.

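### SAP 4.1.5 and 4.2 make meeting all eligibility criteria a condition of ITT, where the protocol's ITT is all enrolled patients: a minor wording conflict to correct

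*SAP*

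**What the plan says.** **Protocol, section 6, Analysis populations.** "The intent-to-treat (ITT) population will include all enrolled patients". No eligibility condition is attached. The same section adds "A per-protocol population will not be defined for this study", and it foresees deviations at entry: "all major deviations (at study entry and on study) will be summarized and reported". ITT is the main efficacy set unless it differs from the Safety population by five or fewer patients.

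**SAP 4.1.5.** "The ITT population will include all patients who have signed informed consent and met all eligibility criteria". The section cites the protocol for the five-patient rule and records that the rule was not triggered, so ITT is the set used for efficacy. It mentions no change in the definition of ITT.

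**SAP 4.2**, under a sub-heading for enrolled patients. "Number of patients who signed informed consent and met all eligibility criteria, i.e. number of patients in the ITT Population". The next item reports the Safety population as a percentage of ITT.

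**SAP 4.1.4.** The Safety population is every enrolled patient with at least one dose, again with no eligibility condition.

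**The concern.** An ITT set that is conditional on eligibility is narrower than one made up of all enrolled patients whenever someone is enrolled and later found not to qualify. The protocol expects deviations at entry, and neither document says which side of the line such a patient falls on. Taken at its word, the SAP would exclude these patients from OS, PFS, ORR and DCR without saying that it departs from the protocol. No per-protocol set is defined and SAP 4.4.4 plans no formal sensitivity analysis, so the reports would not show the effect.

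The literal wording also breaks the relation between the two populations. A dosed patient later found ineligible would be in Safety but not in ITT, although SAP 4.2 treats Safety as a part of ITT.

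**Working it through.** **1. The plan's own figure.** The sample-size section gives a precision of ±0.5% for 5 events in 1000. The exact Clopper-Pearson limits are 0.163% and 1.163%, so the half-width is (1.163 − 0.163)/2 = 0.500%, which reproduces it. This figure concerns AE rates in the Safety population and does not depend on the ITT definition.

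**2. The two definitions in symbols.** Let E be all enrolled patients, U those eligible but undosed, I_u those ineligible and undosed, and I_d those ineligible but dosed.

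| Set | Protocol | SAP, literal |
|---|---|---|
| ITT | E | E − I_u − I_d |
| Safety | E − I_u − U | E − I_u − U |
| ITT minus Safety | U + I_u | U − I_d |

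- Under the protocol, Safety always lies inside ITT. Under the literal SAP wording, the I_d patients are in Safety only. The ratio (E − I_u − U)/(E − I_u − I_d) is then not a proper proportion, and it exceeds 1 when I_d > U.
- The five-patient comparison depends on the definition. For example, 16 ineligible undosed patients add 16 to the difference under the protocol and 0 under the literal SAP wording.
- If I_u = I_d = 0, the definitions coincide.

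**3. The only rate in the documents.** Protocol 1.3.3, on the earlier Phase II study: "486 patients were screened and 316 patients were enrolled into IMvigor 210"; "five enrolled patients later did not meet eligibility criteria and were not dosed with study drug"; "Ongoing responses were recorded in 38 (84%) of 45 responders".

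- Rate: 5/316 = 1.58%, exact 95% CI 0.52% to 3.65%.
- ORR in that study: 45/316 = 14.24% on all 316, and 45/311 = 14.47% without the five, a shift of about 0.2 points.

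**4. Scaled to this trial.** Assumptions: 1000 enrolled, 150 responders, the whole ITT set as denominator, the same rate, and all such patients undosed and therefore non-responders (SAP 4.4.2.3).

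- Expected number: 1000 × 0.0158 ≈ 16 (range 5 to 37 from the CI).
- All enrolled: 150/1000 = 15.00%, 95% CI 12.8% to 17.4%.
- Without them: 150/984 = 15.24% (range 150/995 = 15.08% to 150/963 = 15.58%).
- Shift: about +0.2 points (range 0.1 to 0.6), well inside the CI.

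OS and PFS would hardly move, because SAP 4.4.2.1 and 4.4.2.2 censor never-treated patients at day 1.

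**5. If some of them were dosed.** The direction is unknown. As a purely assumed range, take 1% to 5% ineligible, with none or 30% of them responding. With 50 removed, ORR is 150/950 = 15.8% or (150 − 15)/950 = 14.2%. That is at most about 0.8 points either way.

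**The case against.** The best defence is that the SAP phrase is shorthand for enrolled. SAP 4.2 uses it under the sub-heading for enrolled patients. Protocol 4.5.1 requires eligibility to be confirmed before enrollment, and Protocol 9.2 forbids eligibility waivers. The Safety-out-of-ITT percentage makes sense only if ITT is everyone enrolled, which suggests that the literal reading was not intended. SAP 4.1.5 also applies the protocol's five-patient rule with no sign of having changed the set. All of this stands, and it is why the point is minor. It does not rescue the text. The words state a condition that the protocol does not have, and they give no rule for ineligibility discovered after enrollment.

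It is also fair that visibility is partly planned. SAP 4.2 lists enrolled patients and major violations by patient, so what is missing is a rule on population membership, not all reporting.

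Three stronger readings are tempting and not supported:

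- *A reader might infer that the protocol's own usage proves that enrolled includes patients later found ineligible.* Its usage is mixed. Section 1.3.3 counts 316 enrolled in the earlier study, including the five. Sections 1.3.2 and 3.3.8 give 311 as the enrolled number for the same patients. It is also a different study.
- *A reader might infer from the ITT–Safety gap of more than five that such patients exist here.* The gap can consist entirely of eligible patients who were never dosed. On the literal SAP wording, ineligible undosed patients are in neither set and cannot contribute to it.
- *A reader might take the SAP 4.6.2 coding of ECOG 2 at screening but 3 at baseline as evidence of ineligible patients.* It does not show that, because the deciding timepoint may be screening.

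**Conclusion.** Minor, but wrong as written: SAP 4.1.5 and 4.2 state an ITT definition that departs from Protocol section 6 without saying so. If the phrase is a paraphrase, no result changes. If it was programmed literally, the efficacy denominators lose enrolled patients with eligibility deviations, and Safety need not be a subset of ITT.

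The number of such patients in this trial is not given and may be zero. The estimate of about 0.2 ORR points rests on three borrowed or assumed inputs: the earlier study's 1.6% rate, all such patients undosed, and an ORR of 15%. The documents do not support a claim of material bias. All analyses are descriptive, efficacy is secondary, and the primary AE endpoint uses the Safety population, whose definition is not in question.

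**What to change.** In SAP 4.1.5 and 4.2, replace the definition with: *ITT = all enrolled patients (enrolled through IxRS), regardless of eligibility deviations identified later.* Protocol 9.5 already names IxRS as the enrollment route. Then confirm that the programmed ITT flag and the five-patient comparison with Safety used this definition, and report how many enrolled patients, if any, fall outside the flag. If the phrase was only a paraphrase, that number is zero and no output changes.

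The cost is two SAP sentences, one check of the flag and one reported count. No new data are needed.

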4.2 ANALYSIS OF STUDY CONDUCT

Disposition of patients

Patients will be considered as having treatment discontinued when the “Study Completion/Early Discontinuation” has been captured for the treatment phase.

Patients will be considered as having discontinued/completed the study when the “Study Completion/Early Discontinuation” has been captured for the follow-up phase or the treatment phase and it was indicated as the final study period.

The disposition of patients will be summarized as follows:

Enrolled patients:

- Number of patients who signed informed consent and met all eligibility criteria, i.e. number of patients in the ITT Population

- Number and percentage of patients who have received at least one dose of atezolizumab, i.e. number and percentage of patients in the Safety Population (out of the ITT Population)
- Number and percentages of patients who have permanently discontinued atezolizumab, overall and by reasons for discontinuation (out of the Safety Population)
- Number and percentages of patients who have permanently discontinued atezolizumab by cycle and by reasons for discontinuation (out of the Safety Population). Discontinuations will be associated with the number of cycles the patient received, a cycle being counted when dose >0. A summary table and figure will be provided.
- Number and percentages of patients who have discontinued the study, overall and by reasons for discontinuation (out of the ITT Population)
- Number and percentages of patients by region, country and site number (out of the ITT population and Safety population)

Following by-patient listing including site, patient identifier and relevant data will be provided:

- Enrolled patients

Protocol violations

A by-patient listing of major protocol violations will be provided.

4.3 ANALYSIS OF BASELINE CHARACTERISTICS

Demography and baseline characteristics will be summarized using descriptive statistics and frequency tables, respectively, based on the safety population at Baseline.

A baseline value will be defined as the last available value before or on the date of first study drug administration, as follows:

- Assessment with a date prior to the date of first study drug administration
- Assessment with a date equal to the date of first study drug administration, if either
 - It is the screening/baseline visit
 - In case of assessments on the same date as the drug administration, it will be assumed that these were performed before the actual time of drug intake.

Demography:

- Descriptive statistics of age in years, age categories (<65, ≥65 -<85 and ≥85 years), age categories (<80 and ≥80 years)
- Frequency tables of sex, ethnicity and race

Baseline characteristics

- Non-cancer General Medical History
 - Number and percentages of patients with history of any medical condition overall and by status of medical condition and by System Organ Class (SOC) and Preferred Terms (PT)
- History of Cancer
 - Descriptive statistics of time from primary diagnosis to start of study treatment, frequency tables of histological tumor type, non-urothelial tumors sub-type, squamous neoplasms sub-type, glandular neoplasms sub-type, neuroendocrine sub-type, histological grade, location, TNM classification and stage of tumor at primary diagnosis and at study entry, descriptive statistics of time from primary diagnosis to diagnosis of metastatic disease
- Prior Tumor Surgery
 - Frequency of patients with prior tumor surgery before entering the study
 - Frequency tables of surgery setting and surgery purpose
- Prior Cancer Radiotherapy
 - Frequency tables therapy setting and given boost
- Prior Systemic Cancer Therapy
 - Frequency tables of therapy intent, highest line of therapy, and information regarding platinum treatment. Patients who received prior adjuvant/neoadjuvant chemotherapy will be considered as having 0 lines of treatment for metastatic disease (irrespective of the line(s) of therapy entered in eCRF).
- General Surgery and Procedure History (Non-Cancer)
 - Number and percentages of patients with any relevant surgeries or procedures
- Autoimmune disease
 - Number and percentages of patients who have any history of autoimmune disease
 - Number and percentages of patients with resolved diseases, ongoing diseases with treatment and ongoing diseases without treatment
- Serology Local
 - HIV test
 - Number and percentages of patients with negative, positive and not done HIV tests
 - Number and percentages of patients with a final negative or positive HIV tests
 - Descriptive statistics of HIV Load for final positive HIV tests
 - Number and percentages of patients suffering from AIDS

- Hepatitis Testing
 - Number and percentages of patients with negative, positive and not done tests regarding Hepatitis B Surface Antigen
 - Number and percentages of patients with negative, positive and not done tests regarding Anti Hepatitis B Core Antibody
 - Number and percentages of patients with negative, positive and not done tests regarding Anti Hepatitis B Surface Antibody
 - Number and percentages of patients with negative, positive and not done tests regarding anti-HCV Antibody
 - Number and percentages of patients with negative, positive and not done tests regarding anti-HCV RNA
 - Number and percentages of patients with negative, positive and not done tests regarding anti-HBV DNA
- Female Reproductive Status and Local Pregnancy Test
 - Frequency table of female reproductive status
 - Frequency table of sample type (urine, serum)
 - Frequency of patients with a final negative or positive test result
- Tobacco Use History
 - Number and percentages of patients by tobacco use history and by sex (males vs females)
 - Descriptive statistics of smoking duration in years
- Electrocardiogram (ECG)
 - Descriptive statistics of heart rate [beats/min], PQ (PR) duration [ms], QRS duration [ms], QT duration [ms], QTcF [ms]
 - Frequency table of ECG result
- Eastern cooperative oncology group (ECOG) Performance Status
 - Frequency table of ECOG score
- Age-adjusted Charlson Comorbidity Index (AACI)
 - Descriptive statistics of the calculated total score
 - Frequency table of the calculated total score
- Brain magnetic resonance imaging/computed tomography (MRI/CT) status
 - Frequency of patients with knowledge, symptoms or suspicion of central nervous system (CNS) metastases
 - Frequency of patients with performed MRI/CT Scan
 - Frequency of patients with present metastasis
 - Descriptive statistics of number of metastasis
- Renal impairment at baseline

- Descriptive statistics of creatinine clearance
- Frequency of patients with/without renal impairment
- PD-L1 expression
 - PD-L1 expression by IHC class (IC0 to IC3)
 - PD-L1 expression: IC0/1 or IC2/3

Renal dialysis reported at baseline is defined as 'No' for all patients included with protocol version < 5 (regardless if any or no dialysis reported or no information given). For patients included with protocol version 5 or higher, if patient reports dialysis at Screening or Cycle 1 Day 1, then renal dialysis is set to 'Yes', otherwise if no dialysis is reported or if information is missing then renal dialysis is set to 'No'.

The time from diagnosis of primary disease to start of study treatment will be calculated in units of years as the difference between the date of start of study treatment and date of diagnosis of primary disease plus 1, divided by 365.25. For the calculation of the time from diagnosis of primary disease to start of study treatment, replacement rules will be applied in case the date of diagnosis of primary disease is incomplete. If day and month are missing, they will be imputed by June 30th to allow for time calculation, if only the day is missing, it will be imputed by 15. If after imputation, the date of diagnosis of primary disease is later than the start date of study treatment, then it will be set to the start date of study treatment.

The time from diagnosis of primary disease to diagnosis of metastatic disease will be calculated in units of years as the difference between the date of occurrence of metastatic disease and date of diagnosis of primary disease plus 1, divided by 365.25. For the calculation of the time from diagnosis of primary disease to diagnosis of metastatic disease, replacement rules will be applied for both dates in case dates are incomplete. If day and month are missing, they will be imputed by June 30th, if only the day is missing, it will be imputed by 15. If after imputation, the date of diagnosis of primary disease is later than the date of diagnosis of metastatic disease, then it will be set to the date of diagnosis of metastatic disease.

Creatinine clearance at baseline will be calculated using the Cockcroft-Gault formula:

$$\text{Creatinine clearance}[\text{mL / min}] = \frac{(140 - \text{age}[\text{years}]) \times \text{weight}[\text{kg}] \times (0.85 \text{ if female or } 1.0 \text{ if male})}{72 \times \text{serum creatinine}[\text{mg / dL}]}$$

A patient will be defined as having renal impairment in case creatinine clearance at baseline is < 30 mL/min.

By-patient listing of demographic and baseline characteristics as listed above will be provided based on the Safety Population. Prior intravesical therapy will also be listed.

For assessments listed above performed at baseline and post-baseline timepoints, the corresponding listings will include both baseline and post-baseline assessments.

Derivations for selected prior platinum regimens are as follows (on regimens level):

Selected prior platinum regimens	
Gemcitabine + Cisplatin	If patient has at least one combination of (Gemcitabine or Gemcitabine hydrochloride) + Cisplatin within a prior systemic cancer therapy
Gemcitabine + Carboplatin	If patient has at least one combination of (Gemcitabine or Gemcitabine hydrochloride) + Carboplatin within a prior systemic cancer therapy
Methotrexate + Vinblastine + Cisplatin + Adriamycin (MVAC)	If patient has at least one combination of (Methotrexate or Methotrexate sodium) + Vinblastine + Cisplatin + (Adriamycin or Doxorubicin or Doxorubicin hydrochloride) within a prior systemic cancer therapy
Methotrexate + Vinblastine + Cisplatin (MCV)	If patient has at least one combination of (Methotrexate or Methotrexate sodium) + Vinblastine + Cisplatin, not together with (Adriamycin or Doxorubicin or Doxorubicin hydrochloride) nor (Epirubicin or Epirubicin hydrochloride), within a prior systemic cancer therapy
Methotrexate + Vinblastine + Cisplatin + Epirubicin (MVEC)	If patient has at least one combination of (Methotrexate or Methotrexate Sodium) + Vinblastine + Cisplatin + (Epirubicin or Epirubicin hydrochloride) within a prior systemic cancer therapy

Derivations for selected regimens for patients who never had prior platinum are as follows (on patient-level)

Patients who never had prior platinum regimens	Number of patients
Patients with Single-agent Gemcitabine	If patient has at least one prior systemic cancer therapy with Gemcitabine or Gemcitabine Hydrochloride alone
Patients with Single-agent Vinflunine	If patient has at least one prior systemic cancer therapy with Vinflunine alone
Patients with Other Regimens	If patient has neither therapy with Gemcitabine or Gemcitabine Hydrochloride alone nor Vinflunine alone but any other non-platinum based prior systemic cancer therapy

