#### **4.1.1 Inclusion Criteria**

Patients must meet the following criteria for study entry:

1. Signed informed consent form
2. Age  $\geq$  18 years
3. Is, according to the investigator's judgment, able to comply with the study protocol
4. Histologically documented locally advanced (T4b, any N; or any T, N 2–3) or metastatic (M1, Stage IV) urothelial or non-urothelial carcinoma of the urinary tract
  - Urinary tract carcinoma includes carcinoma of the bladder, ureter, urethra, and renal pelvis
  - Primary non-urothelial carcinoma includes all sub-types listed in the WHO classification (see [Appendix 8](#))
    - Bellini collecting duct tumors are allowed if independently reviewed by two expert pathologists from different sites
    - Lymphoma, sarcoma, and renal cell carcinoma are excluded
5. Patients with measurable and/or non-measurable disease according to RECIST v1.1 are allowed
6. Must have progressed during or following treatment with at least one (and not more than 3) prior treatments for inoperable, locally advanced or metastatic urothelial or non-urothelial carcinoma of the urinary tract
  - Patients who received prior adjuvant/neoadjuvant chemotherapy and progressed within 12 months of treatment will be considered as having a first line of treatment for metastatic disease
  - Patients who were intolerant to prior systemic treatment are allowed as long as they had received at least 2 treatment cycles
  - Platinum- or non-platinum-based chemotherapy regimens are allowed
  - Low-dose chemotherapy given as radiosensitizer for curative treatment of localized disease does not count as a line of systemic chemotherapy
7. Representative formalin-fixed paraffin-embedded (FFPE) tumor specimen block available for submission.

- Only tissue from core needle (with  $\geq$  3 cores), punch, incisional, excisional, or forceps biopsies will be accepted. Fine-needle aspiration, brushing, bone tissue, and lavage samples are not acceptable
- If an appropriate tumor specimen is not available, a sample will be collected by biopsy during the study screening period
- ONLY at sites where local laws and regulations prohibit the sending of tumor specimen blocks to an outside central laboratory, specimen slides are acceptable. A minimum of 15 unstained serially-cut sections must be prepared and sent per tumor sample. For details, please refer to the Sample Handling Manual

8. Eastern Cooperative Oncology Group (ECOG) Performance Status 0, 1 or 2

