2.3 DETERMINATION OF SAMPLE SIZE

This is a single-arm safety study. There is no formal statistical hypothesis and all analyses will be descriptive. The results for the primary safety variables will be presented via percentages and corresponding 95% Clopper-Pearson confidence intervals (CIs).

A sample size of approximately 1000 patients is planned for this study. The precision of (e.g., rare) AE incidence estimates presented by two-sided exact 95% Clopper-Pearson CIs are shown in Table 1.

Table 1 Two-Sided Clopper-Pearson 95% Confidence Intervals for Adverse Event Rate Estimates

Number of Patients with at Least One Event (Expected) N=1000	Expected Event Rate (%)	Lower limit of CI (%)	Upper limit of CI (%)
12	1.2	0.62	2.09
10	1.0	0.48	1.83
8	0.8	0.35	1.57
6	0.6	0.22	1.3
5	0.5	0.16	1.16
4	0.4	0.11	1.02
3	0.3	0.06	0.87
2	0.2	0.02	0.72
1	0.1	0.00	0.56

CI = confidence interval.

Therefore, for a sample size of 1000 patients and an expected AE incidence of 0.5%, based on the half-width of the Clopper-Pearson 95% CI, the true AE rate can be estimated with a precision of: $\pm(1.16\% - 0.16\%)/2\% = \pm0.5\%$.

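### As worded, SAP 4.3 sets every patient with prior adjuvant or neoadjuvant chemotherapy to zero metastatic lines, including those later treated for advanced disease

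*SAP*

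**What the plan says.** In SAP 4.3, the item on prior systemic cancer therapy plans "Frequency tables of therapy intent, highest line of therapy, and information regarding platinum treatment". It then states that patients with prior adjuvant or neoadjuvant (below, perioperative) chemotherapy "will be considered as having 0 lines of treatment for metastatic disease (irrespective of the line(s) of therapy entered in eCRF". This is the only derivation the SAP gives for the number of prior metastatic lines.

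Protocol 4.1.1, Inclusion Criterion 6, requires progression during or after "at least one (and not more than 3) prior treatments for inoperable, locally advanced or metastatic urothelial or non-urothelial carcinoma of the urinary tract". Protocol 4.1.2, Exclusion Criterion 1, bars more than three lines. Criterion 6 also treats perioperative chemotherapy as a first metastatic line when progression came within 12 months, and it does not count low-dose radiosensitising chemotherapy. SAP Appendix 1 reprints Criterion 6.

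The derived variable is used in several places:
- SAP 4.4.5: a 0/1/2/3 subgroup for the secondary efficacy endpoints.
- SAP 4.4.5: a split of the PD-L1 adverse event, death and efficacy tables by line, and a separate efficacy breakdown at zero lines.
- SAP 4.4.5: one criterion (0, 1 or 2 lines) of the IMvigor211-like definition.
- SAP 4.6.2: by-patient listings and the adverse event summary repeated by subgroup.

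Protocol 6.6 has a differently named variable with levels 1, 2 and 3 and no level 0.

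**The concern.** A patient can have neoadjuvant chemotherapy, relapse, receive one, two or three regimens for advanced disease, and then enter this study. The SAP sentence sends that patient to level 0 whatever the site recorded.

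Three things follow. Level 0 would combine patients never treated for advanced disease with patients treated up to three times. Levels 1 to 3 would contain only patients who never had perioperative chemotherapy, a selected group. The IMvigor211-like flag could admit a patient whose line count should fail it. Tables by line would then not describe what their labels say, and pretreatment is one of the first things a reader will look at in this population.

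**Working it through.** **Scope of the rule.** The subject of the sentence is the patient: "Patients who received prior adjuvant/neoadjuvant chemotherapy will be considered as having 0 lines of treatment for metastatic disease". It does not restrict itself to patients whose sole treatment was perioperative, sets no time window and makes no exception for later regimens. No other SAP section narrows it. Elsewhere in 4.3 the SAP states the unit of its prior-therapy derivations: "Derivations for selected prior platinum regimens are as follows (on regimens level" and "Derivations for selected regimens for patients who never had prior platinum are as follows (on patient-level". The line rule carries no such label.

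**Eligible histories.** Take a patient with one perioperative regimen. Let m be the number of regimens for advanced disease, and let e = 1 if progression came within 12 months of the perioperative regimen, otherwise 0. The count under Criterion 6 is m + e, and entry requires 1 to 3. A site applying Criterion 6 would enter m + e as the highest line. Six (e, m) pairs qualify; (0, 0) gives 0 and (1, 3) gives 4, so both are excluded.

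| e | m | Entered line, m + e | Literal SAP | Count by intent, m |
|---|---|---|---|---|
| 1 | 0 | 1 | 0 | 0 |
| 1 | 1 | 2 | 0 | 1 |
| 1 | 2 | 3 | 0 | 2 |
| 0 | 1 | 1 | 0 | 1 |
| 0 | 2 | 2 | 0 | 2 |
| 0 | 3 | 3 | 0 | 3 |

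**Comparison, conditional on m being the intended quantity.**
- Literal SAP: differs from m in 5 of 6 histories, by 1, 2, 1, 2 and 3 levels. The 0-to-2-line criterion is wrongly met in one, (0, 3).
- Sentence removed and entered lines used: differs in 3 of 6, namely (1, 0), (1, 1) and (1, 2). The line criterion is wrongly failed in one, (1, 2), entered as 3.
- Entered lines used but perioperative-only patients kept at 0: differs in 2 of 6, namely (1, 1) and (1, 2).
- Regimen-level count by intent: equals m by construction.

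**Example.** For history (1, 1), neoadjuvant chemotherapy with early progression is entered as line 1, and one regimen for metastatic disease is entered as line 2. The literal SAP gives 0, the entered highest line is 2, and the count by intent is 1.

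These are logical cases, not patients.

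**The case against.** The strongest reply is that the narrow reading is the sensible one. Criterion 6 would lead sites to enter early-progressing perioperative chemotherapy as line 1, and the parenthesis in SAP 4.3 looks designed to undo that entry. A level 0 exists in 4.4.5 and 4.6.2, and the IMvigor211-like definition pairs 0 to 2 lines with platinum progression within 12 months; both fit that purpose. I accept this as the probable intent. It does not rescue the text, because two programmers could follow the same sentence to different datasets.

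The case counts are open to fair criticism. They weight histories equally, assume one perioperative regimen per patient, and take m as the target, which is inferred. Against the Criterion 6 count, m + e, the proposed count differs in 3 of 6 histories, the three with e = 1. The presence of a level 0 shows that the SAP does not intend m + e, since that count is never 0 in an eligible patient, but the target still has to be written down. The argument from the unit labels is also weak, since those labels head separate derivation tables.

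A reader might infer that the reported tables are wrong, or that five in six patients with perioperative chemotherapy are misclassified. The documents support neither. They do not show the program, and they do not give the frequency of any of these histories.

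The impact is also limited. The SAP states that "There is no formal statistical hypothesis and all analyses will be descriptive". Therapy intent is tabulated, and a "By-patient listing of demographic and baseline characteristics as listed above will be provided based on the Safety Population", so individual histories can be checked.

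**Conclusion.** The point holds as a defect of wording with real consequences if the wording is followed. It is a misstated rule rather than a missing detail: the stated rule assigns the wrong level to eligible patients who had perioperative chemotherapy and then treatment for advanced disease, by one to three levels each.

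The size in patients is unknown and I offer no estimate. The affected outputs are the line subgroups for efficacy and safety, the PD-L1-by-line and zero-line tables, and the IMvigor211-like flag. That flag is wrongly met on lines only at exactly three advanced-disease lines, and such a patient must still satisfy every other criterion of the definition. Overall estimates and the whole-population incidence of treatment-emergent adverse events do not depend on the variable. It would be wrong to read this as a threat to the primary result.

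The conclusion rests on the literal text and on the protocol admitting the histories described. That the variable should count regimens for advanced disease is inferred from its name and its level 0. The point is worth correcting because the fix is cheap and the variable is widely used.

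**What to change.** Reword the rule in SAP 4.3 to regimen level:
- Adjuvant and neoadjuvant regimens, identified by recorded therapy intent, and low-dose radiosensitising chemotherapy do not count as metastatic lines, whatever line number was entered.
- Every other systemic regimen for inoperable, locally advanced or metastatic disease counts.
- Level 0 means no counted regimen. Defining it as perioperative therapy alone would leave unclassified a patient who also had a radiosensitiser.

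Do not simply delete the sentence and use entered lines; that brings back perioperative regimens entered as line 1.

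Add one sentence saying that this count differs from the 12-month rule in Inclusion Criterion 6 and from the 1/2/3 subgroup in Protocol 6.6.

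Then check the program. If it already counts by regimen, the cost is the wording alone. If it follows the literal text, re-derive the line-based tables and the IMvigor211-like flag. The SAP tabulates therapy intent and derives platinum combinations within a single prior therapy, so regimen-level data appear to exist. The eCRF is not among the documents, so confirm that intent is recorded for each regimen and that radiosensitising use can be identified.
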